3. GENERAL DATA ANALYSIS CONSIDERATIONS

3.1 Analysis Set(s)

The ITT Analysis Set will consist of all enrolled and randomized women, and all enrolled infants. Participant treatment for mothers will be determined according to their randomization arm assignment. Participant treatment for infants will be determined according to their mother's randomization arm assignment.

A secondary Product Exposure Set will be used for some analyses and will differ from the ITT Analysis Set in that participants who never received any study product (per the Pharmacy Dispensation CRF) and endpoints that occur $>$ 7 days after study product discontinuation (per the Discontinuation of Study Product CRF) will be excluded.

A secondary Infant Exposure Set will be used for some analyses and will be the same as the ITT Analysis Set except that infants whose mothers never received study product will be excluded. If all enrolled and randomized mothers in a cohort received study product then the Infant Exposure Set and Infant ITT Analysis Set will be identical, and analyses using the Infant Exposure Set will not be performed.

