6.2 Treatment Exposure

As described in Section 3.1 Analysis Set(s), the Product Exposure analysis set will exclude endpoint data that occurs > 7 days after study product discontinuation, and will exclude participants who never received study product.

Study duration, infant study duration, on product duration, on study pregnancy duration, and estimated gestational age at pregnancy outcome will be summarized as continuous variable in tables, by study arm and overall for each of the three cohorts, and for the three cohorts combined.

Study duration will be calculated as the date of study exit (Study Termination CRF) minus the participant's randomization date + 1 day, unless the participant had a termination reason of "Lost to follow-up". If a participant was lost to follow-up then their study duration will be calculated as the date of their last attended visit minus their randomization date + 1 day. The last attended visit is either the last visit with a completed Follow-up Visit Summary CRF, or the last Interim Visit Summary CRF where at least one study procedure was completed (per Interim Visit Summary CRF, "What study procedures were completed at this visit? Select all that apply" item), whichever occurred last.

Infant study duration will be calculated as the date of study exit (Study Termination CRF) minus the infant's birth date + 1 day, unless the infant had a termination reason of "Lost to follow-up". If an infant was lost to follow-up then their study duration will be calculated as the date of their last attended visit minus their birth date + 1 day. The last attended visit is either the last visit with a completed Infant Follow-up Visit Summary CRF, or the last Infant Interim Visit Summary CRF where at least one study procedure was completed (per Interim Visit Summary CRF, "What study procedures were completed at this visit? Select all that apply" item), whichever occurred last.

On product duration will be calculated as the date of product discontinuation (Discontinuation of Study Product CRF) minus the participant's randomization date + 1 day. Only participants who ever received study product will be included in this summary.

On study pregnancy duration will be calculated as the date of the pregnancy outcome (outcome date on Pregnancy Outcome CRF) minus the participant's randomization date + 1 day. Only participants with an obtainable pregnancy outcome will be included in this summary.

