8.1 Primary Maternal Safety

The primary maternal safety endpoint is all maternal adverse events that were either serious adverse events (SAEs) or were Grade 3 or higher. These are referred to in this document as “composite AEs”.

The number and percentage of participants experiencing at least one composite AE and the exact binomial confidence intervals for those proportions will be summarized by study arm and overall for each of the three cohorts (including an exploratory analysis that splits Cohort 3 based on gestational age as described in Section 5), and by study arm and overall for the three cohorts combined. This analysis will include all participants in the ITT Analysis Set.

Secondary analyses will be conducted to further explore maternal safety. These analyses include:

1. The analyses in the preceding paragraph will be repeated using the Product Exposure Set
2. Summaries of the total number of primary maternal safety endpoints reported per participant, by study arm and overall for each of the three cohorts (including a summary of the two Cohort 3 subgroups defined in Section 5), and by study arm and overall for the three cohorts combined. This will use the ITT Analysis Set.
3. A Poisson regression model will be fitted comparing the number of primary maternal safety endpoints per participant by arm, adjusted for site, with an offset of the number of days from randomization to study product discontinuation (see “on product duration” definition in Section 6.2). This model will be fitted for all cohorts combined only, and will use the ITT Analysis Set.

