8.2 Primary Infant Safety

The primary infant safety endpoint is all infant adverse events that were either SAEs or were Grade 3 or higher. These are referred to in this document as “composite AEs”.

The number and percentage of infants experiencing at least one composite AE and the exact binomial confidence intervals for those proportions will be summarized by study arm and overall for each of the three cohorts (including an exploratory analysis that splits Cohort 3 based on gestational age as described in Section 5), and by study arm and overall for the three cohorts combined. This analysis will include all infants in the ITT Analysis Set (as appropriate given the cohort/study arm being summarized).

Secondary analyses will be conducted to further explore infant safety. These analyses include:

1. The analyses in the preceding paragraph will be repeated using the Infant Exposure Analysis Set.
2. Summaries of the total number of primary infant safety endpoints reported per infant, by study arm and overall for each of the three cohorts (including a summary of the two Cohort 3 subgroups defined in Section 5), and by study arm and overall for the three cohorts combined. This will use the ITT Analysis Set.
3. A Poisson regression model will be fitted comparing the number of primary infant safety endpoints per participant by arm, adjusted for site, with an offset of the number of days from birth to study termination (see “infant study duration” definition in Section 6.2). This model will be fitted for all cohorts combined only, and will use the ITT Analysis Set.

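### The maternal Poisson model in SAP 8.1 counts events over all of follow-up but time only to product discontinuation, and pools cohorts with different allocation ratios without a cohort term

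*SAP*

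**What the plan says.** SAP 8.1 defines the count broadly: "The primary maternal safety endpoint is all maternal adverse events that were either serious adverse events (SAEs) or were Grade 3 or higher". Secondary analysis 3 models the number of these events per woman by arm, adjusted for site, "with an offset of the number of days from randomization to study product discontinuation". It adds: "This model will be fitted for all cohorts combined only, and will use the ITT Analysis Set".

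The pieces it relies on are defined elsewhere in the SAP:

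- **Analysis set (3.1).** "The ITT Analysis Set will consist of all enrolled and randomized women, and all enrolled infants". No event is dropped on grounds of timing. A timing rule exists only for the Product Exposure Set, where "endpoints that occur $>$ 7 days after study product discontinuation (per the Discontinuation of Study Product CRF) will be excluded".
- **Exposure time (6.2).** "On product duration will be calculated as the date of product discontinuation (Discontinuation of Study Product CRF) minus" the randomization date, plus one day. On who is included: "Only participants who ever received study product will be included in this summary".
- **Full maternal follow-up (6.2).** Study duration, from randomization to study exit (or to the last attended visit for women lost to follow-up), is defined but not used in this model.
- **End of product use and of follow-up.** Section 2.1 ends product use at the pregnancy outcome at the latest. Appendix II (Tables 8 to 10) puts the maternal exit visit at 42 days after the outcome, 13 days either side.
- **Infant model (8.2).** The parallel model uses full follow-up: "with an offset of the number of days from birth to study termination".
- **Allocation (2.1, 2.3).** 2:1 ring to tablet in Cohorts 1 and 2, 4:1 in Cohort 3.

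**The concern.** A Poisson rate is interpretable only if events and time cover the same period. Here the events run to study exit and the time stops at product discontinuation. About six weeks after the outcome add events and no time. The SAP itself expects events in that period: postpartum hemorrhage, puerperal sepsis and endometritis are listed complications, and each enters the composite when serious or Grade 3 or higher.

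Two consequences follow for the comparison of arms. First, discontinuation happens after randomization and can be prompted by an adverse event. An arm in which more women stop early loses person-time but keeps their later events, so its apparent rate rises with no change in risk. Second, the inflation is largest where on-product time is shortest, in Cohort 1, and smallest in Cohort 3. The arms contain different mixes of cohorts and the model adjusts for site only, so the inflation does not cancel between arms.

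This is the only between-arm model that the SAP specifies for maternal safety.

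**Working it through.** The SAP gives no rate, rate ratio or power for this model, so there is no figure to reproduce. The check compares person-days on product (the planned offset) with person-days on study.

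**Inputs from the SAP.** Planned sizes, ring:tablet: 100:50, 100:50 and 200:50 (2.1 regimen text, Table 1). The design line in 2.1 lists 150 women for Cohort 3, but the 200:50 split and the total of about 550 imply 250, which is used here. Exit is 42 days after the outcome, window 29 to 55 (Appendix II).

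**Assumptions, not in the SAP.** Enrolment at 37, 33 and 21 weeks in Cohorts 1, 2 and 3; outcome at 39 weeks (range 38 to 40); constant event rate per study day; true rate ratio 1; nobody stops early.

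**Step 1, days per woman.** On product = (39 − enrolment week) × 7 + 1; on study = on product + 42.

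| Cohort | On product | On study | Inflation of rate |
|---|---|---|---|
| 1 | 15 | 57 | 3.8 |
| 2 | 43 | 85 | 2.0 |
| 3 | 127 | 169 | 1.3 |

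**Step 2, totals by arm.**
- Ring, on product: 100×15 + 100×43 + 200×127 = 31,200. On study: 100×57 + 100×85 + 200×169 = 48,000. Inflation 48,000/31,200 = 1.54.
- Tablet, on product: 50×(15 + 43 + 127) = 9,250. On study: 50×(57 + 85 + 169) = 15,550. Inflation 15,550/9,250 = 1.68.

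**Step 3, apparent rate ratio.** 1.538/1.681 = 0.915 when the truth is 1. Outcome at 38 weeks with exit at 55 days gives 1.775/2.006 = 0.885; outcome at 40 weeks with exit at 29 days gives 1.341/1.422 = 0.943.

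**Step 4, simulation.** 400 simulated trials (arm-only model, enrolment uniform within each cohort's gestational range, exit 42 days after outcome, true ratio 1) gave a mean rate ratio of 0.93 with the on-product offset and 1.01 with the study-duration offset.

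**Step 5, source of the shift.** Cohort 3 is 200/400 = 50% of the ring arm and 50/150 = 33% of the tablet arm. Within a cohort, with equal stopping, both arms are inflated by the same factor, so a cohort term returns the ratio to 1.00. The shift in Step 3 therefore needs both the mismatch and the missing cohort term.

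**Step 6, is the offset alone enough?** Suppose instead that event risk per woman is equal in all cohorts, with 21, 45 and 120 on-product days (assumed). Mean on-product days are 76.5 (ring) and 62 (tablet), so the ratio is 62/76.5 = 0.81. Adding 42 days to each gives 104/118.5 = 0.88. Study duration without a cohort term still leaves a shift; with one, the ratio is 1.00.

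**Step 7, unequal stopping.** If a fraction d of one arm in Cohort 3 stops halfway, with follow-up and risk unchanged, that arm's apparent rate is multiplied by 1/(1 − d/2): 1.05 at d = 10%, 1.11 at 20%, 1.18 at 30%. A cohort term does not remove this; matching events and time does.

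**The case against.** The strongest reply is that little hangs on the model. It is the third secondary analysis. The primary analysis is the proportion of women with an event and its exact interval, which no offset touches. Section 2.6 plans no direct testing between arms for the primary analyses. The first two secondary analyses already give proportions on the Product Exposure Set and event counts per woman. This stands, and it limits the severity.

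Several stronger readings are tempting but not supported:

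- **That the on-product offset by itself produces the 0.92.** It does not: with equal stopping, a cohort term removes that shift (Step 5). Nor would a study-duration offset alone always suffice (Step 6).
- **That single early stoppers distort the ratio many-fold.** A woman who stops on day 7 of 169 study days has her own rate inflated about 24-fold (169/7), but Poisson regression does not average individual ratios. The pooled effect is that of Step 7, and the SAP documents no stopping rate or arm difference.
- **That never-dispensed women are silently excluded.** The restriction in 6.2 governs a descriptive summary. For the model, their handling is unstated, and there may be no such women.
- **That the offset should not be in days.** Naming days as the offset is ordinary shorthand under a log link; writing log(days) is a clarification.
- **That the Poisson variance is wrong.** Overdispersion is possible, but the SAP gives no basis for its size.

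Two caveats remain. The SAP does not say in so many words that events are counted to study exit; this follows from the ITT set having no cut-off. A limit on adverse event reporting in the protocol could shorten the period, but only a limit at discontinuation would remove the mismatch, and the 7-day rule in 3.1 presupposes that later events are collected. Also, study duration is not perfectly clean: under 2.1, women who acquire HIV stay at least twelve months on a modified schedule.

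**Conclusion.** The concern holds as a moderate one that should be fixed. As written, 8.1 secondary analysis 3 pairs an unrestricted ITT event count with a time at risk that ends at product discontinuation and is undefined for any woman never dispensed product. That mismatch follows from the text and needs no assumption.

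Its size does need assumptions. With no early stopping, the ring-to-tablet rate ratio is about 0.92 (0.89 to 0.94) when the true value is 1, under the constant rate and the enrolment, outcome and exit times stated above. Part of the cause is the pooling of 2:1 and 4:1 cohorts with adjustment for site only. In these scenarios the shift makes the ring look safer. Unequal stopping would add a further shift in either direction, of unknown size.

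A reader might infer that the trial's primary maternal safety results are compromised. They are not: the proportions and exact intervals do not use this offset.

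**What to change.** In 8.1 secondary analysis 3:

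1. For the ITT model, replace the offset with log(study duration) as defined in 6.2, in line with the infant model. Every randomized woman then has a value.
2. Add a cohort term alongside site.
3. State the date to which events are counted, including for women in extended follow-up after HIV acquisition, and end the time at risk on the same date.
4. If an on-product rate is wanted, fit it as a separate model on the Product Exposure Set, with events up to 7 days after discontinuation and an offset of log(on-product days + 7, capped at study exit).

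Robust standard errors are an optional safeguard, not part of the correction.

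The cost is a few lines of SAP text and a small program change. Study duration, on-product duration and cohort are already derived or recorded, so no new data are needed. The primary analysis is unchanged.

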8.2 Primary Infant Safety

The primary infant safety endpoint is all infant adverse events that were either SAEs or were Grade 3 or higher. These are referred to in this document as “composite AEs”.

The number and percentage of infants experiencing at least one composite AE and the exact binomial confidence intervals for those proportions will be summarized by study arm and overall for each of the three cohorts (including an exploratory analysis that splits Cohort 3 based on gestational age as described in Section 5), and by study arm and overall for the three cohorts combined. This analysis will include all infants in the ITT Analysis Set (as appropriate given the cohort/study arm being summarized).

Secondary analyses will be conducted to further explore infant safety. These analyses include:

1. The analyses in the preceding paragraph will be repeated using the Infant Exposure Analysis Set.
2. Summaries of the total number of primary infant safety endpoints reported per infant, by study arm and overall for each of the three cohorts (including a summary of the two Cohort 3 subgroups defined in Section 5), and by study arm and overall for the three cohorts combined. This will use the ITT Analysis Set.
3. A Poisson regression model will be fitted comparing the number of primary infant safety endpoints per participant by arm, adjusted for site, with an offset of the number of days from birth to study termination (see “infant study duration” definition in Section 6.2). This model will be fitted for all cohorts combined only, and will use the ITT Analysis Set.

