2.1 General Design Considerations

The following is a summary of Protocol Version 2.0

Short Title:	DELIVER: A Phase 3b Safety Study of the Dapivirine Ring and PrEP in Pregnant Women
IND Sponsor:	DAIDS
Funders:	Division of AIDS, NIAID, NIMH, NICHD, US NIH
Protocol Chair:	[name], MPH [name], MMed
Protocol Co-Chair:	[name], FCPaeds
Sample Size:	Approximately 550 women and their infants
Study Population:	Healthy, HIV-uninfected pregnant females, 18-40 (inclusive) years old, with an uncomplicated singleton pregnancy who are willing to be randomized to study product, and their infants
Study Sites:	MTN-042 site(s) selected by the MTN Executive Committee
Study Hypotheses:	
 • Daily use of Truvada oral tablet and dapivirine (DPV) vaginal matrix ring (25 mg) inserted once every 4 weeks will both be generally safe and well-tolerated by the participants and their fetuses/infants. • Participants who use Truvada oral tablet daily and insert the DPV vaginal matrix ring (25 mg) once every 4 weeks will experience similar distributions of pregnancy outcomes to the general population.
Study Design:	Phase 3b, two-arm, open label, multi-site, randomized (2:1) trial (DPV vaginal ring [VR], Truvada oral tablet), with onset of dosing period to occur within the following gestational age (GA) ranges: 
Cohort 1: 36 0/7 weeks – 37 6/7 weeks 150 women Cohort 2: 30 0/7 weeks – 35 6/7 weeks 150 women Cohort 3: 12 0/7 weeks – 29 6/7 weeks 150 women

Study Duration:	The total duration of study participation for each participant will vary depending on gestational age at time of enrollment and length of pregnancy prior to pregnancy outcome, and will range from approximately 12 weeks or less for Cohort 1 to approximately 36 weeks or less for Cohort 3. Participants who

become infected with HIV will continue in study follow-up with a modified study visit/procedure schedule for a minimum of twelve months. Also, infants born to MTN-042 participants will be followed for approximately 52 weeks (i.e., one year)

Study Products:

- Silicone elastomer matrix VR containing 25 mg of DPV
- Oral tablets (Truvada) containing 200 mg emtricitabine/300 mg tenofovir disoproxil fumarate (FTC/TDF)

Study Regimen:

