An alternative way of describing the statistical properties of the study design is in terms of the 95% confidence interval for the “true” rate based on the observed data. The table below shows the exact 2-sided 95% confidence intervals for the probability of an event based on a particular observed rate. For example, if none of the 400 participants receiving the VR regimen experience a safety event, the 95% exact 2-sided upper confidence bound for the true rate of such events in a particular arm of the study is 0.92%.

Table 2. Confidence intervals for endpoint rate (proportion of participants with endpoint) given number of endpoints (rows) in with number of participants (columns)

Number of events	Number of participants ^a				
	n=50	n=100	n=150	n=200	n=400
0	0.00, 7.11	0.00, 3.62	0.00, 2.43	0.00, 1.83	0.00, 0.92
1	0.05, 10.65	0.03, 5.45	0.00, 3.66	0.01, 2.75	0.00, 1.38
2	0.49, 13.71	0.24, 7.04	0.16, 4.73	0.12, 3.57	0.06, 1.79
3	1.25, 16.55	0.62, 8.52	0.41, 5.73	0.31, 4.32	0.15, 2.18
4	2.22, 19.23	1.10, 9.93	0.73, 6.69	0.55, 5.04	0.27, 2.54
5	3.33, 21.81	1.64, 11.28	1.09, 7.61	0.82, 5.74	0.41, 2.89

Number of events	Number of participants ^a				
	n=50	n=100	n=150	n=200	n=400
6	4.53, 24.31	2.23, 12.60	1.48, 8.50	1.11, 6.42	0.55, 3.24
8	7.17, 29.11	3.52, 15.16	2.33, 10.24	1.74, 7.73	0.87, 3.90
10	10.03, 33.72	4.90, 17.62	3.24, 11.92	2.42, 9.00	1.21, 4.55
12	13.06, 38.17	6.36, 20.02	4.20, 13.56	3.14, 10.25	1.56, 5.18
15	17.86, 44.61	8.65, 23.53	5.71, 15.96	4.26, 12.07	2.11, 6.11
20	26.41, 54.82	12.67, 29.18	8.34, 19.84	6.22, 15.02	3.08, 7.62
30	45.18, 73.59	21.24, 39.98	13.92, 27.30	10.35, 20.72	5.12, 10.53

^aSample sizes in the table based on the proposed cohort size and study design.

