8. PRIMARY ENDPOINTS

An intent to treat analysis will be performed to summarize the frequency of primary endpoints (maternal safety, infant safety and pregnancy outcome) by study arm (ITT Analysis Set). An additional analysis will be conducted including only visits in which a participant has been exposed to the study product (Product Exposure Set). Analyses will be conducted separately for each of the three cohorts (including an exploratory analysis that splits Cohort 3 based on gestational age as described in Section 5), with a final aggregate analysis that will include all enrolled participants from each of the three cohorts. The number and the percentages of participants experiencing each primary endpoint will be tabulated by study arm. Each participant will contribute once in each category (i.e., only for highest severity AE for each

participant) for the calculation of event rates. Exact binomial confidence intervals will be calculated for each primary endpoint. Primary endpoint event rates will be compared to baseline estimates from MTN-042B by checking whether the baseline estimates are included in the exact binomial confidence intervals (this will not be included as part of the CSR). A secondary analysis will be performed to summarize the total number of primary and secondary safety endpoints reported per participant by study arm.

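### The primary infant safety percentage counts infants lost without a recorded event as event-free, so as a 52-week risk it is biased low to the extent of loss

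*SAP*

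**What the plan says.** Section 3.1 fixes the population: "The ITT Analysis Set will consist of all enrolled and randomized women, and all enrolled infants". Section 8.2 takes as the primary infant result "The number and percentage of infants experiencing at least one composite AE and the exact binomial confidence intervals for those proportions", and adds: "This analysis will include all infants in the ITT Analysis Set". Section 8 applies the same interval method throughout: "Exact binomial confidence intervals will be calculated for each primary endpoint". Section 8.1 is built in the same way for mothers.

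Section 2.1 says that "infants born to MTN-042 participants will be followed for approximately 52 weeks". Section 6.2 expects that some will be lost and defines their observed time: "If an infant was lost to follow-up then their study duration will be calculated as the date of their last attended visit", counted from birth. That duration enters the analysis of the primary infant endpoint only as the offset of a secondary Poisson model (8.2, third secondary analysis), which compares arms for all cohorts combined. Neither 8.1 nor 8.2 sets a minimum follow-up, a censoring rule or a time-to-event estimate for the percentages.

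Section 2.6 shows how the interval is meant to be read. Its example begins "if none of the 400 participants receiving the VR regimen experience a safety event, the 95% exact 2-sided upper confidence bound" and gives 0.92% as a bound on the true event rate.

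**The concern.** The numerator can hold only events that were seen, while the denominator holds every enrolled infant. An infant who leaves at two weeks with nothing recorded carries the same weight as one observed for a year without an event. Recorded events are a subset of those that occurred, so as an estimate of risk over planned follow-up the percentage can be right or too low, but not too high. The exact interval has the same fault, because it treats each infant as fully observed.

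The primary objective is to describe the safety profile, and an error that runs only toward looking safer matters there. Section 2.6 invites readers to take the interval as one for the true rate, which goes further than a count of recorded events.

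**Working it through.** **Inputs.** From the SAP: the all-enrolled denominator (3.1, 8.2), the exact two-sided 95% interval (2.6, 8), and about 52 weeks of follow-up (2.1). Assumed, because the SAP states neither: a true 52-week risk R = 15% and a share lost d of 2%, 5%, 10% or 20%, with loss unrelated to outcome.

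**The plan's own figure.** With 0 events in n, the exact upper bound is 1 − 0.025^(1/n). For n = 400 it is 0.92%, as printed.

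**Reported percentage under loss.** Reported = (1 − d) × R + d × r, where r is the average risk accrued before loss.

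- Loss soon after birth: r = 0.
- Loss spread evenly, constant hazard: λ = −ln(0.85) = 0.1625, and r = 1 − R/λ = 1 − 0.15/0.1625 = 7.70%.
- Loss spread evenly, 70% of the hazard in the first 6 weeks: r found numerically.

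| Share lost (assumed) | Soon after birth | Even, constant hazard | Even, early hazard |
|---|---|---|---|
| 2% | 14.70% | 14.85% | 14.94% |
| 5% | 14.25% | 14.64% | 14.85% |
| 10% | 13.50% | 14.27% | 14.70% |
| 20% | 12.00% | 13.54% | 14.41% |

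Example at 10%, even loss: 0.90 × 15% + 0.10 × 7.70% = 13.50% + 0.77% = 14.27%.

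**Zero-event bound.** If the lost share contributes no information, 0/400 becomes 0/360 at 10% loss (0.92% rises to 1.02%) and 0/320 at 20% (1.15%). For n = 150, 2.43% becomes 2.70% (0/135) and 3.03% (0/120).

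**Against sampling error.** The exact interval for 60/400 (15%) is 11.65% to 18.88%, roughly 3.6 points either side. For 15/100, Table 2 prints 8.65% to 23.53%. A shortfall of 0.15 to 0.3 points at 2% loss is minor. One of 3.0 points (20% lost soon after birth) is close to the half-width at n = 400.

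**Does the remedy work for infants?** Every infant has the same planned horizon, and death is part of the composite, so it does not compete with it. In simulation at R = 15% with 10% and 20% non-informative loss, 1 − Kaplan-Meier at 52 weeks returned about 15%.

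**Does it work for mothers?** Section 2.1 puts maternal participation at about 12 weeks or less in Cohort 1 and 36 or less in Cohort 3. A simulated ring arm (100, 100 and 200 women in the three cohorts) had no loss at all, with enrollment spread evenly over each gestational-age window and delivery assumed at about 39.3 weeks (SD 1.5). The true proportion with an event was about 14% to 15%. The pooled 1 − Kaplan-Meier at 36 weeks was about 26% to 28%, whether the hazard was constant or events fell in the week after delivery. The curve treats women who completed a short planned follow-up as censored and still at risk.

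**The case against.** The strongest reply is that the SAP is descriptive (3.2) and the crude percentage is a standard AE summary, valid as the proportion of enrolled infants with a recorded event. That stands, and it is why the crude figure should stay. It does not settle the matter, because 2.6 presents the interval as one for the true rate and 8.2 does not label the figure as recorded events.

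Second, loss will be visible: the plan has a CONSORT diagram per cohort (6.1), durations by arm (6.2) and retention tables (6.5), and the infant Poisson model uses observed time. This is also true, but none of it gives an absolute risk by arm and cohort that allows for loss.

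Third, Kaplan-Meier assumes that loss is unrelated to outcome, which may fail. That is a reason to show it beside the crude figure and state the assumption.

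A reader might also infer several stronger points that the document does not support:

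- **Everyone who withdrew or was lost is counted as event-free.** An event recorded before loss counts.
- **Section 8.3 contradicts 8.1 by limiting its denominator to obtainable pregnancy outcomes.** A pregnancy with no obtainable outcome cannot be classified as term, preterm or loss, whereas dropping those women from 8.1 would discard AEs already seen.
- **Mothers need the same time-to-event remedy.** The simulation shows that it would nearly double the stated risk even with no loss.

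**Conclusion.** The point holds for infants. As an estimate of risk over about 52 weeks, the 8.2 percentage and its exact interval are biased low to the extent of loss. With a true risk of 15%, the shortfall runs from about 0.15 points (2% lost, evenly) to 3.0 points (20% lost, all soon after birth). It is smaller still if events cluster in the first weeks. Both the risk and the loss rates are assumptions. A reader might conclude that the reported risks will be materially too low, but without a loss rate in the SAP that cannot be shown.

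For mothers the same denominator logic applies, and the maternal Poisson offset is on-product time, so it does not account for follow-up after discontinuation. The workable remedy there is labelling and, at most, a sensitivity percentage.

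This is a worthwhile and cheap improvement to a descriptive analysis. The crude percentage remains valid for what it counts.

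**What to change.** **Infants (8.2).**

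- Label the crude figure as the proportion of enrolled infants with a recorded composite AE.
- Always report beside it, by arm and cohort, the cumulative incidence of a first composite AE (1 − Kaplan-Meier, 95% CI) to about 52 weeks from birth, censored at the infant study duration of 6.2.
- State that this assumes non-informative loss.
- Fix the time horizon in advance. The 12-month window in Appendix II opens 28 days before day 365, so infants can complete from day 337.
- Do not let the choice of headline estimate depend on whether anyone terminated early, since a single dropout would then switch it.

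**Mothers (8.1).** Keep the crude percentage, labelled as recorded events. Do not add a pooled Kaplan-Meier from randomization. At most, add a sensitivity percentage among women followed to the 6-week post-outcome visit or with an earlier event. Note that this version can overstate risk, because early leavers enter its denominator only if they had an event.

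**Cost.** A wording change and one extra infant table from dates already derived, with no new data. The stated infant risk will be slightly higher and its interval slightly wider. If retention is near complete, the two figures will agree and the table will show that the crude percentage can be relied on.
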